1.2 Primary Objectives

- 1.2.1 To estimate the optimal dosing frequency of depot MPA (DMPA) for HIV and TB coinfecting women taking EFV-based combination antiretroviral therapy (cART) and RIF-containing TB treatment based on a target MPA concentration >0.1 ng/mL.
- 1.2.2 To determine whether a 150 mg DMPA IM injection will be adequate to suppress ovulation through 12 weeks in women taking EFV-based cART and RIF-containing TB treatment based on serial plasma progesterone concentrations.

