3.0 STUDY DESIGN

A5338 is an open-label, non-randomized 12-week, single-arm study to determine the PK of single-dose DMPA among women with TB and HIV co-infection who are receiving RIF-containing TB treatment plus EFV-based cART. Biomarkers of suppression of ovulation will also be evaluated. Participants will be HIV and TB co-infected women who have completed the intensive phase and are already in the continuation phase of RIF-containing TB treatment and who have been on EFV-based cART for at least 4 weeks.

Women diagnosed with TB and who are not already receiving HIV treatment at the time of screening for eligibility may start cART at any time between 2 and 8 weeks after TB treatment has been initiated, at the discretion of the treating physician and health care provider at the local clinic and in accordance with national and local treatment guidelines. Women who develop TB while on ART may also participate in the study. At study entry, all participants will receive a single IM injection of DMPA.

We will estimate individual MPA elimination rates, and then examine if any participant has a plasma progesterone level >5 ng/mL by the time that the estimated MPA level reaches 0.1 ng/mL. If data allows, a correlation between plasma progesterone levels and MPA concentrations observed at study weeks 10 and 12 will be investigated to better understand a minimum threshold of MPA concentration level to prevent ovulation using plasma progesterone level. If MPA clearance is induced by the co-administered drugs, the study week 10 and later are thought to be the times when ovulation would be most likely to occur, and increased plasma progesterone levels would be seen.

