We will estimate MPA area under the concentration-time curve (AUC) by collecting PK samples from baseline (week 0) pre-DMPA dosing through week 12 after DMPA dosing from all participants. We will determine whether potential PK interactions between EFV-based cART with RIF and DMPA affect the suppression of ovulation as measured by the proportion of participants whose progesterone level is >5 ng/mL at weeks 2, 4, 6, 8, 10, and 12. We will also determine the proportion of women who have sub-therapeutic concentrations of MPA (levels <0.1 ng/mL) at different time points. Using a combination of both sub-therapeutic concentrations of MPA and progesterone >5 ng/mL, we will be able to determine whether contraception is thought to be maintained throughout the 12-week study. Mathematical modeling will be employed to determine the optimal frequency of DMPA dosing in the setting of TB and HIV cotreatment.

Information about demographic factors that can affect drug concentrations such as age, sex, ethnicity, disease state, and concomitant drug use will be collected on all participants. Whole blood will be collected and stored for potential pharmacogenomics analyses including CYP2B6 genotyping. All participants will be strongly encouraged to use condoms and non-hormonal contraceptives for prevention of pregnancy and sexually transmitted infections (STI) if engaging in behaviors that put them at risk. The participants will be informed that the contraceptive effect of DMPA may be attenuated and participants who engage in activities that could lead to pregnancy will be required to use another non-hormonal contraceptive. Other forms of hormonal contraceptives will be prohibited. Women who have had a tubal ligation or other sterilization procedure, are currently using a non-hormonal intrauterine device (IUD) or those whose partners have had a vasectomy will be eligible for the study.

All participants will complete self-reported questionnaires to assess adherence to both TB therapy and cART, and to collect AEs commonly reported with DMPA, ie, irregular bleeding patterns. Adherence will also be assessed by review of patients' TB treatment records and participant's self-report.

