9.6.1 Analyses of Primary Outcome Measurements

The proportion of participants with sub-therapeutic MPA levels (<0.1 ng/mL) will be estimated based on the participants who complete the PK sampling at 12 weeks after DMPA administration. A 90% confidence interval (CI) will be provided for proportion using Clopper-Pearson exact method for binomial measurements. This CI will provide us reasonable evidence that the true proportion is greater than the threshold (6%), by determining whether the 90% CI is entirely above the threshold.

Individual-specific MPA concentration-time curves in the elimination phase will be estimated by fitting \log_e -linear regression models to the data of MPA concentrations obtained at time of maximum MPA concentration and later. These estimated individual elimination curves will then be used to estimate the times (weeks) where MPA concentration levels reach at 0.1 ng/mL. We will present descriptive statistics of these estimated weeks including mean, SD, median, interquartile range, minimum and maximum. Mixed-effects model analysis (allowing individual elimination slope to be both fixed and random variable) with repeated measurements within individual participants will also be performed to estimate the times for comparison purposes with the results obtained using the \log -linear regression models fitted for individual participants. These modeling approaches will provide the population mean estimate of the time where MPA concentration level reaches at 0.1 ng/mL with 90% CI, which will guide us to determine optimal dosing frequency of DMPA in the study population. Details of these modeling approaches will be described in the statistical analysis plan that will be generated separately and approved by study team.

Descriptive statistics of plasma progesterone levels will be tabulated by study week. If there are participants with progesterone levels >5 ng/mL, the proportion and percentage of participants with progesterone levels >5 ng/mL will be tabulated by study week.

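### Primary objective 1.2.2 asks about ovulation suppression through 12 weeks, but the stated progesterone summaries are by week, with no per-woman proportion and no interval

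*Protocol*

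**What the plan says.** Objective 1.2.2 (Protocol 1.2) is to determine whether a 150 mg injection "will be adequate to suppress ovulation through 12 weeks in women taking EFV-based cART and RIF-containing TB treatment based on serial plasma progesterone concentrations". Section 9.2.1 lists progesterone at weeks 2, 4, 6, 8, 10 and 12 as a primary outcome measure.

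For that outcome, section 9.6.1 plans three things:

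- Descriptive statistics of progesterone by study week, without any condition.
- A threshold table that is conditional. It opens "If there are participants with progesterone levels >5 ng/mL" and then says that "the proportion and percentage of participants with progesterone levels >5 ng/mL will be tabulated by study week". No interval is stated.
- Exploratory plots and nonlinear models of progesterone against MPA at weeks 10 and 12, aimed at finding a lower therapeutic limit for MPA.

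Section 3.0 says that suppression will be "measured by the proportion of participants whose progesterone level is >5 ng/mL at weeks 2, 4, 6, 8, 10, and 12", with no condition attached. It also describes two per-woman intentions. One is to "examine if any participant has a plasma progesterone level >5 ng/mL by the time that the estimated MPA level reaches 0.1 ng/mL". The other begins "Using a combination of both sub-therapeutic concentrations of MPA and progesterone >5 ng/mL" and is meant to show whether contraception was maintained throughout the study. Section 9.6.1 gives neither of them a summary.

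The MPA proportions are treated differently. Sections 9.6.1 and 9.6.2.3 give exact 90% Clopper-Pearson intervals at week 12 and, as secondary analyses, at weeks 8 and 10.

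Section 9.6 describes itself as a summary and promises a detailed plan. The supplied SAP states that it addresses secondary objectives 1.3.1 and 1.3.2, and it contains no progesterone analysis. None of the changes listed in the amendment letters or clarification memos touches 9.6.1.

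**The concern.** Suppression through 12 weeks is a property of each woman's whole series of results. A by-week proportion is a property of each visit. Once any woman is positive, the visit-level figures do not determine the woman-level figure, so the stated summaries cannot answer the objective as worded.

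The case with no positives is a plausible one. Section 9.4 reports that, in two earlier studies, none of the five women with MPA below 0.1 ng/mL at 12 weeks showed evidence of ovulation. In that case 9.6.1 produces no threshold table and no statement of uncertainty. A run of weekly zeros can then be read as showing that the injection is adequate, when a sample of this size cannot exclude a true proportion of several percent.

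The week-12 MPA result does not fill the gap. Those same five women show that low MPA and ovulation are different events.

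**Working it through.** **Inputs.** n = 42 evaluable women and 46 enrolled, one-sided alpha 0.05, null 6%, alternative 21%, rejection at 6 or more (all section 9.4). The interval method is the 90% Clopper-Pearson interval of 9.6.1. The progesterone event counts below are assumptions, because the documents give no expected ovulation rate.

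**1. The plan's own figure, which concerns MPA.** For an exact binomial with n = 42 and rejection at 6 or more:

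- P(X ≥ 6 | 6%) = 0.038
- P(X ≥ 6 | 21%) = 0.901

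The stated 90% power reproduces. The 90% lower limit is 6.4% at 6/42 and 4.8% at 5/42, so the stated equivalence between the test and the interval also holds. The documents give no corresponding figure for progesterone.

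**2. What weekly counts reveal about women.** With complete data, the number of women ever positive lies between the largest weekly count (the same women each time) and the sum of the weekly counts (different women each time). Take one positive at week 10, one at week 12 and none before. The largest weekly count is 1 and the sum is 1 + 1 = 2.

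The 90% Clopper-Pearson limits for x of n are:

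- lower = Beta quantile 0.05 with parameters (x, n − x + 1)
- upper = Beta quantile 0.95 with parameters (x + 1, n − x)

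| Who is positive | Weekly table | Women ever positive | 90% CI |
|---|---|---|---|
| Same woman twice | 1/42, 1/42 | 1/42 = 2.4% | 0.1 to 10.8% |
| Two women once each | 1/42, 1/42 | 2/42 = 4.8% | 0.9 to 14.2% |

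The weekly table is the same in both rows.

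**3. No positives.** The upper limit solves (1 − p)^n = 0.05, so p = 1 − 0.05^(1/n).

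- n = 42: 1 − 0.05^(1/42) = 6.9%
- n = 46: 1 − 0.05^(1/46) = 6.3%

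The chance of seeing no positive woman among 42 when the true per-woman proportion is p is (1 − p)^42:

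- p = 2%: 0.98^42 = 42.8%
- p = 3%: 0.97^42 = 27.8%
- p = 5%: 0.95^42 = 11.6%

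**The case against.** **Another plan may cover it.** Section 9.6 is avowedly a summary, and the SAP limits itself to two secondary objectives. A reader might infer that objective 1.2.2 was left without an adequate analysis altogether. The documents do not support that. They show only that the supplied text lacks a per-woman summary and an interval.

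**Progesterone is not left to the conditional table alone.** A reader might infer that it is. In fact the by-week descriptive statistics are unconditional, and 3.0 states the by-visit proportion without a condition. If the descriptive statistics show the maximum and the number of women, anyone can see that there were no events and work out 0/n and its limit. That is fair, and it makes the zero case the smaller part of the problem. It does not help once someone is positive.

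**Description may be deliberate.** Section 9.4 makes the week-12 MPA proportion the primary analysis outcome and sizes the study on it. Describing progesterone without a test is defensible in a single-arm phase II PK study. That stands as a reason not to ask for a test, but an interval is not a test.

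**The ambiguity can be made to look larger than it is.** One positive at each of six visits would span 2.4% to 14.3%. That pattern sits badly with 3.0, where "the study week 10 and later are thought to be the times when ovulation would be most likely to occur", and with 2.1.1, which puts peak MPA within 3 weeks of injection. Likewise, the 9.8% loss quoted in 9.4 is week-12 specimen or assay loss in another study. The documents give no basis for applying it independently at every visit to obtain wide missing-data bounds.

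**Conclusion.** The point holds in a limited form. In the supplied documents, a primary objective about suppression through 12 weeks is summarised by week, with the threshold table conditional on events and without an interval. The summary does not identify the per-woman proportion.

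On a realistic assumed pattern (one positive at each of weeks 10 and 12 among 42 women), the same table fits 2.4% or 4.8%, with upper limits of 10.8% or 14.2%. With no positives, the unstated upper limit is 6.9% for 42 women or 6.3% for 46. These figures rest on assumed counts and complete follow-up.

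The powered MPA analysis is unaffected. A reader might also infer that 1.2.2 should be judged against 6%. The documents do not support that, because the 6% is a rate of low MPA and no acceptable ovulation rate is given. Confidence is medium, since a plan for the primary objectives may exist outside the supplied documents.

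**What to change.** In 9.6.1, or in whichever plan covers the primary objectives:

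- **Main summary for 1.2.2.** Report the proportion of women with any progesterone above 5 ng/mL from week 2 through week 12, with a 90% Clopper-Pearson interval, also when the count is zero. Cite the upper limit in any statement on adequacy. Keep the weekly table as supportive.
- **Denominator.** Use women with progesterone results through week 12, plus any woman with an observed value above 5 ng/mL before leaving. This avoids scoring early leavers as suppressed. It also keeps the focus on women still taking EFV and RIF, which replaced women may not be. Adding only the positive early leavers pushes the estimate slightly upward, so report how many dosed women had incomplete follow-up. The MPA proportion in 9.6.1 is "based on the participants who complete the PK sampling at 12 weeks after DMPA administration", so the two denominators may differ and should both be shown.
- **Sensitivity analysis.** Use all dosed women with at least one post-dose result, counting gaps at week 10 or 12 first as negative and then as positive.
- **Alongside.** Report pregnancies, so that a woman who conceived without an observed high value is not lost from view.

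No adequacy bound is proposed.

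The cost is a few extra lines of analysis and a stated upper limit that looks slightly less favourable than a row of weekly zeros. All the data are already scheduled for collection.

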9.6.2 Analyses of Secondary Outcome Measurements

9.6.2.1 Estimation of MPA PKs in presence of EFV and RIF:

MPA PK parameters AUC_{0-12wk} , concentration at week 12 (trough concentration, C_{min}), C_{max} , CL/F , and $T_{1/2}$ will be estimated using non-

compartmental approach and descriptive statistics of these PK parameters will be presented. For the purpose of evaluating whether these PK parameters are significantly different from those in women not on the companion drugs, those PK parameters will be compared to those from the historic controls (A5093 Control Arm) using nonparametric two-sample Wilcoxon test. GMRs in MPA PK parameters of co-administration over administration-alone and associated 90% CIs will also be presented to provide magnitude of the differences as a supplementary analysis.

9.6.2.2 Estimation of time and variability in time to reach a MPA 0.1 ng/mL:

Times (weeks) and variability in times to reach MPA 0.1 ng/mL will be estimated using the analysis methods described in section 9.6.1.

9.6.2.3 Estimation of the proportion of participants reaching MPA level <0.1 ng/mL:

The proportion and percentage of participants with MPA concentration levels <0.1 ng/mL will be summarized by each of the study weeks 8 and 10. 90% CI for proportion at each week will be presented using Clopper-Pearson exact method.

9.6.2.4 Evaluation of toxicity and safety:

Signs and symptoms, chemistry and hematology with toxicity Grade ≥ 3 will be tabulated by study week.

9.6.3 Analyses of Exploratory Outcome Measurements

9.6.3.1 Inter-individual differences in PK parameters between EFV, DMPA, and/or RIF when stratified by human genetic variants that are known to predict altered pharmacokinetics of EFV (eg, CYP2B6) and RIF (eg, SLCO1B1) will be investigated using descriptive statistics of PK parameters categorized by metabolizer status (based on the human genetic variants) and performing a nonparametric ordered test (eg, Jonckheere-Terpstra trend test) in PK parameters for the priori ordering of metabolizer groups in the co-administration if data allows.

9.6.3.2 Associations of MPA PK parameters with baseline BMI and/or body fat percentage will be examined using visual plots (eg, scatter plots) and investigated using linear or nonlinear regression models. Changes of BMIs and body fat percentages at study week 12 from baseline will be descriptively summarized.

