1.4 Exploratory Objectives

- 1.4.1 To explore whether pharmacokinetic (PK) interactions between EFV, RIF, and/or DMPA are affected by human genetic polymorphisms that have been reported to affect metabolism of these drugs.
- 1.4.2 To explore body mass index (BMI) and body fat content over time and correlate with DMPA levels.
- 1.4.3 To explore relationship between DMPA and bone metabolism in the HIV and TB coinfecting women.

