(NNRTIs) and protease inhibitors (PIs) have demonstrated significant interactions with combined oral contraceptives (COC), which might lead to decreased efficacy of the COC [22, 23]. Studies of interactions between ART and DMPA have not demonstrated any clinically significant changes in the levels of either selected cARTs or DMPA. Cohn et al. showed that there were similar levels of DMPA in women on selected cART regimens (nelfinavir [NFV], nevirapine [NVP] and EFV) compared to women not on cART [16, 24]. Another small study done recently also failed to show significant changes in the PK of DMPA in HIV-infected women on cART with zidovudine (ZDV), lamivudine (3TC), and EFV [19]. This cART combination did not increase DMPA-related adverse events nor did it decrease the effectiveness of DMPA [19]. DMPA has not been shown to significantly alter the levels of antiretroviral drugs. The levels of EFV remained unchanged compared to baseline in the Cohn et al. study [16]. Current guidelines do not recommend changes in dosing frequency for patients on EFV-containing cART who use DMPA.

It is unknown whether simultaneous treatment of HIV and TB affected the serum concentration, efficacy, or adverse effects (AEs) of DMPA.

There have been concerns about decreased effectiveness of DMPA in obese women. No pregnancies were documented in two large phase 3 trials that included 193 women (of 1787 total) with a body mass index (BMI) of >30 [25]. A detailed study designed to assess the efficacy of DMPA in obese women revealed fluctuating estrogen levels consistent with follicular development, but no evidence of ovulation [26]. Patients being treated for both TB and HIV may experience even more variability in estrogen and DMPA levels. Patients treated for TB typically gain weight. The proportion of fat gain in that setting is variable and may affect DMPA metabolism. In the exploratory objective, BMI and body fat content will be estimated over time and compared to DMPA levels.

Safety Profile:

DMPA is safe in HIV infected women. There were few toxicities in the ACTG A5093 study related to DMPA with abnormal menstrual bleeding being the most frequent and similar to non-HIV-infected populations [16, 24]. Watts et al. demonstrated no significant changes in the levels of circulating HIV viral load in patients after administration of DMPA [24].

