6.3.5 Clinical Assessments

In addition to the visits specified in section 6.1, the clinical assessments (except height) should be performed when clinically indicated.

Complete Physical Exam

A complete physical examination will be conducted at screening and as part of clinical assessments performed when clinically indicated. The complete physical exam will include, at a minimum, an examination of the skin, head, mouth, and neck; auscultation of the chest; cardiac exam; abdominal exam; examination of the lower extremities for edema; and Karnofsky performance test. It will also include signs and symptoms, diagnoses, and vital signs (weight, height, temperature, pulse, respiration rate, and blood pressure).

Targeted Physical Exam

A targeted physical examination is required at all study visits after screening. The targeted physical exam must include vital signs (temperature, pulse, respiration rate, and blood pressure) and is to be driven by any previously identified or new signs or symptoms including diagnoses that the participant experienced.

Height

Height required to be reported on the CRF at study entry only.

Weight

Weight required at study entry and at all visits.

Waist Circumference

Waist circumference required at study entry and all on-study visits.

Signs and Symptoms

At entry, all grades that occurred 30 days before entry must be recorded in the source document and CRFs.

After entry:

- Grades 1 and 2 toxicities must be recorded in the source document.
- Grades 3 and 4 toxicities must be recorded in both the source document and CRF.
- Record all signs and symptoms that led to a change in treatment regardless of grade on both source document and CRF. Further evaluation will be required for those events that meet Expedited Adverse Event (EAE) or ICH reporting requirements.

Diagnoses

At the entry and post-entry visits, record all diagnoses identified by the ACTG criteria for clinical events and other diseases in the source document and CRFs.

HIV and TB Treatment Modifications

After entry, all modifications to antiretroviral medications and TB drugs including initial doses, subject-initiated, physician modifications and/or protocol-mandated interruptions, modifications, and permanent discontinuation will be recorded on the CRFs.

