9.2.3 Exploratory Outcome Measures

9.2.3.1 Human genetic variants/polymorphisms that are known to affect PK of EFV (eg, CYP2B6) and RIF (eg, SLCO1B1).

9.2.3.2 Participants' BMIs and body fat percentages collected over the study period of 12 weeks. Body fat percentages will be estimated using age, body weight, height, and waist circumference.

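### Objective 1.4.2 asks how BMI and body fat over time relate to DMPA levels, but section 9.6.3.2 relates MPA PK parameters only to baseline values

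*Protocol*

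**What the plan says.** Protocol section 1.4.2 states the objective: "To explore body mass index (BMI) and body fat content over time and correlate with DMPA levels". Section 2.1.1 gives the reason. Patients treated for TB usually gain weight, and "The proportion of fat gain in that setting is variable and may affect DMPA metabolism". The same paragraph repeats the aim: "BMI and body fat content will be estimated over time and compared to DMPA levels".

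The data collection matches that aim. Section 6.3.5 has "Weight required at study entry and at all visits" and "Waist circumference required at study entry and all on-study visits". Section 9.2.3.2 defines the exploratory outcome as "BMIs and body fat percentages collected over the study period of 12 weeks" and explains that "Body fat percentages will be estimated using age, body weight, height, and waist circumference".

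The analysis is in section 9.6.3.2: "Associations of MPA PK parameters with baseline BMI and/or body fat percentage will be examined using visual plots", followed by linear or nonlinear regression. A second sentence provides a descriptive summary of the week-12 change in BMI and body fat. It does not mention MPA.

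Two other places touch body size. Protocol sections 10.1.2 and 10.3 list total, fat and lean weight as covariates in the population PK model, with allometric scaling on total weight or fat-free mass. The SAP scales on total body weight. None of them says whether the value is fixed at baseline or updated by visit.

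**The concern.** The objective, its rationale, the measurement schedule and the outcome definition all concern body size during treatment. The analysis that should answer the objective uses body size before treatment. A woman's BMI at entry shows whether larger women have different MPA exposure. It does not show whether gaining weight or fat over the 12 weeks goes with a change in MPA, which is the question that section 2.1.1 raises.

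What is at stake is one exploratory objective. The team would collect weight and waist at each visit and then have no planned analysis in section 9.6.3.2 that relates the post-entry values to MPA.

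**Working it through.** The plan states no figure on this point, so there is none to reproduce. The check sets the sections side by side, counts measurements, and then gives an illustrative size.

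**1. Which body-size data reach MPA in section 9.6.3.2?**

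- Scheduled visits with weight and waist, entry to week 12 (sections 6.1 and 6.3.5): weeks 0, 2, 4, 6, 8, 10, 12, which is 7 per woman.
- Height is reported at entry only (section 6.3.5), but BMI and body fat percentage can still be computed at every visit from that height, age, and the visit's weight and waist.
- MPA is measured at weeks 2, 4, 6, 8, 10 and 12 (section 9.2.1), so each of the 6 post-entry body-size values has an MPA value from the same scheduled visit.
- Association with MPA: 1 of 7 (week 0).
- Descriptive change: 2 of 7 (weeks 0 and 12), not related to MPA.
- In no section 9.6.3.2 analysis: 5 of 7 (weeks 2 to 10). That is 5 × 42 = 210 of 7 × 42 = 294 for the 42 women in the power calculation, or 5 × 46 = 230 of 7 × 46 = 322 for the 46 to be enrolled.
- Post-entry values related to MPA in section 9.6.3.2: 0 of 6.

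**2. Could the wording mean something else?** The word baseline might be read as attached to BMI alone. The next sentence describes changes from baseline in both measures, which favours baseline for both. On either reading, the change is not linked to MPA.

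**3. Does the SAP fill the gap?** Its introduction limits it to secondary objectives 1.3.1 and 1.3.2. It does not mention 1.4.2, BMI, waist or body fat.

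**4. Illustrative size.** Two inputs are assumptions: an allometric exponent of 0.75 on clearance, and a weight gain of 5% to 10% over 12 weeks. The documents give no 12-week gain for these women. Late MPA is taken as inversely proportional to current clearance. That is reasonable because section 2.1.1 gives a plasma half-life of 24 hours for MPA against about 50 days apparent for the depot.

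- Clearance ratio: 1.05^0.75 = 1.037; 1.10^0.75 = 1.074.
- MPA ratio: 1/1.037 = 0.964; 1/1.074 = 0.931. This is a fall of about 3.6% to 6.9%.

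**5. Against the plan's own yardsticks.**

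- Section 9.4 treats a 30% fall in week-12 MPA as clinically meaningful.
- With the CV of 57% from sections 2.1.1 and 9.4, the log-scale SD is √ln(1 + 0.57²) = 0.53, and the standard error of a mean for 42 women is 0.53/√42 = 0.082. The largest illustrated shift, ln(0.931) = −0.071, is smaller than one standard error.
- Take a lognormal distribution with 6% of women below 0.1 ng/mL (z = −1.555). A shift of 0.071/0.53 = 0.135 moves z to −1.420, so 6% becomes about 7.8%. The alternative in section 9.4 is 21%.

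**The case against.** The best defence has four parts.

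First, the objective can be read as two tasks, describing body size over time and correlating body size with MPA, and section 9.6.3.2 has a sentence for each. AUC, Cmax and CL/F are single values per woman, so a baseline covariate is natural. That explains the choice, but section 2.1.1 says the over-time values are to be compared with DMPA levels, and those levels exist at six visits.

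Second, section 9.6 calls itself a summary with a detailed SAP to follow, and the SAP supplied does not cover even the primary objectives. Its silence on 1.4.2 therefore does not prove that nothing was planned. This stands as a caution. The gap is in the documents available.

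Third, a reader might infer that post-entry body size never reaches MPA anywhere in the plan, or that the population model uses baseline weight and should be switched to visit weight. The documents support neither. Sections 10.1.2 and 10.3 and the SAP leave the timing open, and they do not tie that model to 1.4.2. The SAP also pools two other studies, and nothing shows that visit weights exist for them.

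Fourth, a reader might infer that a weight-driven fall in MPA threatens the main results because it could pass for the drug interaction. The illustrated effect is small, rests on assumed inputs, and is well below the differences the study is sized to detect. A within-woman model would not settle the matter anyway. Every participant takes RIF and EFV, section 2.2 places induction near its maximum at the injection, and there is no unexposed arm.

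**Conclusion.** The mismatch holds, confined to section 9.6.3.2. The objective asks about body size over time in relation to MPA. The analysis relates MPA only to baseline values and leaves the week-12 change unconnected to it. Whether the population PK model uses time-varying size covariates is unclear from the documents.

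The size is minor: one exploratory objective, with none of the 6 post-entry measurements per woman related to MPA in its own analysis. The 3.6% to 6.9% figure depends on the assumed exponent and weight gain. It indicates scale and is not an estimate for this trial. The primary test and the secondary PK comparisons are not called into question. This is a cheap improvement.

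**What to change.** Keep the baseline plots and regressions in section 9.6.3.2 and add one exploratory model:

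- **Outcome:** ln(MPA) at weeks 2, 4, 6, 8, 10 and 12.
- **Terms:** visit week as a category, baseline BMI or body fat percentage, and change from baseline in that measure at the same visit, with a random effect per woman. Categorical week avoids forcing the early peak, which section 2.1.1 places within 3 weeks of injection, onto a straight line.
- **Low values:** a stated rule for MPA below the limit of quantification, since section 10.3 covers this only for the population model.
- **Reporting:** the coefficient for change with its interval, described as an association only. Change in body size arises after the injection, and section 2.1.1 lists weight gain as an effect of DMPA itself. A single-arm model cannot separate weight gain from the drug interaction.

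One added sentence should also say whether the size covariates in the population PK model are fixed at baseline or time-varying. If the team does not want the extra model, narrowing objective 1.4.2 to baseline body size would at least make objective and analysis agree, at the price of leaving the post-entry data unused for this question.

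The cost is a paragraph of plan text and one model on data that A5338 already collects. The downside is limited precision: with 42 to 46 women and small expected changes in body size, the interval for the change term may be wide.
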